4.1 Safety Endpoints

The endpoints for the evaluation of safety are:

- Presence of any unsolicited systemic AEs reported in the 30 minutes after injection of a SP0202 formulation, Prevnar 13, or Pneumovax 23
- Presence of solicited (ie, pre-listed in the participant's DC and in the case report form [CRF]) injection site reactions occurring up to 7 days after the day of injection (D08) of a SP0202 formulation, Prevnar 13, or Pneumovax 23
- Presence of solicited (ie, pre-listed in the participant's DC and in the CRF) systemic reactions occurring up to 7 days after the day of injection (D08) of a SP0202 formulation, Prevnar 13, or Pneumovax 23
- Presence of unsolicited (spontaneously reported) AEs up to 30 days after the day of injection (D31) of a SP0202 formulation, Prevnar 13, or Pneumovax 23
- Presence of SAEs and AESIs, throughout the study period (up to 6-month follow-up)

4.1.1 Adverse Events and Serious Adverse Events

The definitions of an AE, SAE, and the different categories of AEs can be found in Appendix 10.3 of the study protocol.

AEs will be reported by the participants to the investigator, then by the investigator to the Sponsor.

The investigator and any qualified designees are responsible for detecting, documenting, and recording events that meet the definition of an AE or SAE and remain responsible for following up AEs that are serious, considered related to the study intervention or study procedures, or that caused the participant to discontinue the study.

4.1.2 Time Period and Frequency for Collecting AE and SAE Information

Immediate Post-vaccination Observation Period

Participants will be kept under observation for 30 minutes after vaccination to ensure their safety. The post-vaccination observation should be documented in the source document and immediate events will be recorded at D01 in the eCRF.

Reactogenicity

Solicited injection site reactions will be collected from D01 to D08 after vaccination.

Solicited systemic reactions will be collected from D01 to D08 after vaccination.

The solicited injection site reactions and systemic reactions that are pre-listed in the diary cards and CRF, together with the intensity scales, are presented in [Table 4.1](#) and [Table 4.2](#).

Table 4.1: Solicited injection site reactions: terminology, definitions, and intensity scales

CRB term (MedDRA lowest level term [LLT])	Injection site pain	Injection site erythema	Injection site swelling
Diary card term	Pain	Redness	Swelling
Definition	Pain either present spontaneously or when the injection site is touched or injected limb is mobilized	Presence of a redness including the approximate point of needle entry	Swelling at or near the injection site Swelling or edema is caused by a fluid infiltration in tissue or cavity and, depending on the space available for the fluid to disperse, swelling may be either soft (typically) or firm (less typical) to touch and thus can be best described by looking at the size of the swelling

Intensity scale*	CRF: Grade 1: A type of adverse event that is usually transient and may require only minimal treatment or therapeutic intervention. The event does not generally interfere with usual activities of daily living. Grade 2: A type of adverse event that is usually alleviated with additional therapeutic intervention. The event interferes with usual activities of daily living, causing discomfort but poses no significant or permanent risk of harm to the research participant. Grade 3: A type of adverse event that interrupts usual activities of daily living, or significantly affects clinical status, or may require intensive therapeutic intervention. Diary card: Grade 1: No interference with usual activities Grade 2: Some interference with usual activities Grade 3: Significant; prevents usual activities	Grade 1: ≥ 25 to ≤ 50 mm Grade 2: ≥ 51 to ≤ 100 mm Grade 3: > 100 mm	Grade 1: ≥ 25 to ≤ 50 mm Grade 2: ≥ 51 to ≤ 100 mm Grade 3: > 100 mm
-------------------------	---	--	--

MedDRA: Medical Dictionary for Regulatory Activities

* For the subjective reaction of pain, participants will record the intensity scale (Grade 1, 2, or 3) in the diary card. For the measurable reactions of redness and swelling, they will record just the size of the reaction, and the classification as Grade 1, 2, or 3 will be assigned at the time of the statistical analysis.

Table 4.2: Solicited systemic reactions: terminology, definitions, and intensity scales

CRB term (MedDRA lowest level term [LLT])	Fever	Headache	Malaise	Myalgia	Arthralgia	Shivering
Electronic diary card term	Temperature	Headache	Feeling unwell	Muscle aches and pains	Joint pain	Chills
Definition	Elevation of temperature to ≥38.0°C (≥ 100.4°F)	Pain or discomfort in the head or scalp. Does not include migraine.	General ill feeling. Malaise is a generalized feeling of discomfort, illness, or lack of well- being that can be associated with a disease state. It can be accompanied by a sensation of exhaustion or inadequate energy to accomplish usual activities.	Muscle aches and pains are common and can involve more than one muscle at the same time. Muscle pain can also involve the soft tissues that surround muscles. These structures, which are often referred to as connective tissues, include ligaments, tendons, and fascia (thick bands of tendons). Does not apply to muscle pain at the injection site which should be reported as injection site pain.	Pain in a joint or joints	Sensation of cold

Intensity scale*	Grade 1: $\geq 38.0^{\circ}\text{C}$ to $\leq 38.4^{\circ}\text{C}$, or $\geq 100.4^{\circ}\text{F}$ to $\leq 101.1^{\circ}\text{F}$	CRF: Grade 1: A type of adverse event that is usually transient and may require only minimal treatment or therapeutic intervention. The event does not generally interfere with usual activities of daily living.	CRF: Grade 1: A type of adverse event that is usually transient and may require only minimal treatment or therapeutic intervention. The event does not generally interfere with usual activities of daily living.	CRF: Grade 1: A type of adverse event that is usually transient and may require only minimal treatment or therapeutic intervention. The event does not generally interfere with usual activities of daily living.	CRF: Grade 1: A type of adverse event that is usually transient and may require only minimal treatment or therapeutic intervention. The event does not generally interfere with usual activities of daily living.	CRF: Grade 1: A type of adverse event that is usually transient and may require only minimal treatment or therapeutic intervention. The event does not generally interfere with usual activities of daily living.
	Grade 2: $\geq 38.5^{\circ}\text{C}$ to $\leq 38.9^{\circ}\text{C}$, or $\geq 101.2^{\circ}\text{F}$ to $\leq 102.0^{\circ}\text{F}$	 Grade 2: A type of adverse event that is usually alleviated with additional therapeutic intervention. The event interferes with usual activities of daily living, causing discomfort but poses no significant or permanent risk of harm to the research participant.	 Grade 2: A type of adverse event that is usually alleviated with additional therapeutic intervention. The event interferes with usual activities of daily living, causing discomfort but poses no significant or permanent risk of harm to the research participant.	 Grade 2: A type of adverse event that is usually alleviated with additional therapeutic intervention. The event interferes with usual activities of daily living, causing discomfort but poses no significant or permanent risk of harm to the research participant.	 Grade 2: A type of adverse event that is usually alleviated with additional therapeutic intervention. The event interferes with usual activities of daily living, causing discomfort but poses no significant or permanent risk of harm to the research participant.	 Grade 2: A type of adverse event that is usually alleviated with additional therapeutic intervention. The event interferes with usual activities of daily living, causing discomfort but poses no significant or permanent risk of harm to the research participant.

Grade 3: $\geq 39.0^{\circ}\text{C}$ or $\geq 102.1^{\circ}\text{F}$	Grade 3: A type of adverse event that interrupts usual activities of daily living, or significantly affects clinical status, or may require intensive therapeutic intervention. Diary card: Grade 1: No interference with usual activities Grade 2: Some interference with usual activities Grade 3: Significant; prevents usual activities	Grade 3: A type of adverse event that interrupts usual activities of daily living, or significantly affects clinical status, or may require intensive therapeutic intervention. Diary card: Grade 1: No interference with usual activities Grade 2: Some interference with usual activities Grade 3: Significant; prevents usual activities	Grade 3: A type of adverse event that interrupts usual activities of daily living, or significantly affects clinical status, or may require intensive therapeutic intervention. Diary card: Grade 1: No interference with usual activities Grade 2: Some interference with usual activities Grade 3: Significant; prevents usual activities	Grade 3: A type of adverse event that interrupts usual activities of daily living, or significantly affects clinical status, or may require intensive therapeutic intervention. Diary card: Grade 1: No interference with usual activities Grade 2: Some interference with usual activities Grade 3: Significant; prevents usual activities	Grade 3: A type of adverse event that interrupts usual activities of daily living, or significantly affects clinical status, or may require intensive therapeutic intervention. Diary card: Grade 1: No interference with usual activities Grade 2: Some interference with usual activities Grade 3: Significant; prevents usual activities
--	--	--	--	--	--

MedDRA: Medical Dictionary for Regulatory Activities

* For all reactions but fever, participants will record the intensity level (Grade 1, 2, or 3) in the diary card. For fever, they will record the body temperature, and the classification as Grade 1, 2, or 3 will be assigned at the time of the statistical analysis based on the unit used to measure the temperature and the intensity scale.

Unsolicited Non-serious Adverse Events

Unsolicited non-serious adverse events will be collected from D01 to D31 after vaccination.

For measurable unsolicited AEs that are part of the list of solicited reactions, the corresponding scale for solicited reactions will be used.

All other unsolicited AEs will be classified according to the intensity scale provided in the protocol Section 10.3.5.1.2.

Adverse Events of Special Interest (AESIs)

AESIs will be collected throughout the study period, from D01 until 6 months after vaccination.

SAEs

Information on SAEs will be collected and assessed throughout the study, from D01 until 6 months after vaccination.

Medical occurrences that begin before the start of study intervention but after obtaining informed consent will not be recorded on the AE section of the CRF.

All SAEs will be recorded and reported to the Sponsor or designee immediately and under no circumstance should this exceed 24 hours. The investigator will submit any updated SAE data to the Sponsor within 24 hours of it being available.

Investigators are not obligated to actively seek AE or SAE after conclusion of the study participation. However, if the investigator learns of any SAE, including a death, at any time after a participant has been discharged from the study, and he/she considers the event to be reasonably related to the study intervention or study participation, the investigator must promptly notify the Sponsor.

4.1.3 Pregnancy

Pregnancy is an exclusion criterion for enrollment in this study, but a participant could potentially become pregnant during her participation.

- Details of all pregnancies in female participants will be collected after the start of study intervention and until delivery by the investigator and recorded in the Pregnancy CRF. Any data collected after CRF lock will be transmitted to the pharmacovigilance department on the paper form.
- If a pregnancy is reported, the investigator should inform the Sponsor within 1 month of learning of the pregnancy and should follow the procedures outlined in Appendix 10.4 of the protocol.
- Abnormal pregnancy outcomes (eg, spontaneous abortion, fetal death, stillbirth, congenital anomalies, ectopic pregnancy) are considered SAEs.

4.1.4 Adverse Events of Special Interest

An AESI is an event for which ongoing monitoring and rapid communication by the Investigator to the Sponsor must be done. AESI will be collected throughout the study. AESI include the following:

[figure not shown]
- Anaphylaxis defined as per Brighton collaboration case definition (1)

4.2 Immunogenicity Endpoints and Assessment Methods

The endpoints for the evaluation of immunogenicity are:

- Serotype-specific OPA titers for all pneumococcal serotypes included in the SP0202 formulations, as determined by MOPA, at baseline (D01) and 30 days after vaccination (D31)
- Serotype-specific OPA titers ratio (post/pre-injection) for all pneumococcal serotypes included in the SP0202 formulations as determined by MOPA
- Serotype-specific IgG concentrations for all pneumococcal serotypes included in the SP0202 formulations as measured by PnPS-ECL, at baseline (D01) and 30 days after vaccination (D31)
- Serotype-specific IgG concentration ratios (post/pre injection) for all pneumococcal serotypes included in the SP0202 formulations as measured by PnPS-ECL

Multiplexed opsonophagocytic killing assay (MOPA)

This method will be performed on BL0001 and BL0002 collected on D01 and D31 respectively.

Assays will be performed by PPD (a CRO laboratory), Richmond (VA), USA.

Pneumococcal capsular polysaccharide - electro-chemiluminescent assay (PnPS-ECL)

This method will be performed on BL0001 and BL0002 collected on D01 and D31 respectively.

Assays will be performed by Sanofi Pasteur Global Clinical Immunology (GCI), Swiftwater (PA), USA.

4.3 Derived Endpoints: Calculation Methods

4.3.1 Safety

4.3.1.1 Solicited Reactions

4.3.1.1.1 Daily Intensity

All daily records for solicited reactions will be derived into daily intensity according to the following classification: None, Grade 1, Grade 2, Grade 3, or Missing (Unknown).

For the derivation of daily intensities, the following sequential steps will be applied:

- 1) Solicited reactions (except Fever/Pyrexia) with CRF presence recorded as “No” and with all daily records missing (Unknown) then all daily intensities will be derived as None.
- 2) For non-measurable solicited reactions, daily intensities will correspond to daily records reported in the clinical database. For measurable solicited reactions the daily measurements reported in the clinical database will be converted based upon the intensity scales defined in the protocol; this assumes a reaction that is too large to measure (non-measurable, “NM”) is Grade 3. Note: the intensity could be considered “None” (not a reaction) in the analysis despite being considered a reaction by the investigator (eg, swelling measurement > 0 mm but < 25 mm in adults).

Note: The maximum intensity on the ongoing period is derived from the record of the maximum intensity/measurement after the end of the solicited period following the rule described above.

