8.3.2 Method of Detecting AEs and SAEs

Individual diary cards, specifically designed for this study by the Sponsor and provided to the study sites, will be given to study participants for the recording of daily safety information. These diary cards will include pre-listed terms and intensity scales as well as areas for free text to capture additional safety information or other relevant details. Participants will also be provided with rulers for measuring the size of injection site reactions, and with standard digital thermometers for measuring daily temperatures. To ensure consistency of reporting, the study sites will instruct participants on how to correctly use these tools.

At specified intervals, the Investigator or an authorized designee will interview the participants to collect the information recorded in the diary card, and will attempt to clarify anything that is incomplete or unclear. All clinical study information gathered by the study site will be reported electronically by the Investigator or authorized designee using a web-based CRF. Any information that was not documented in the diary card will first be captured in the source document and then reported electronically.

The 6-month follow-up will be done by interviewing participants over the telephone using a questionnaire to capture SAEs and AESIs, if applicable.

The method of recording, evaluating, and assessing causal relationship of AE and SAE and the procedures for completing and transmitting SAE reports are provided in [Appendix 10.3](#).

Care will be taken not to introduce bias when detecting AEs and/or SAEs. Open-ended and non-leading verbal questioning of the participant is the preferred method to inquire about AE occurrences.

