9.4.2 Safety Analyses

Safety analyses will be performed on the SafAS and presented by group and by age group for summary tables (main endpoints). The main parameters will be described with 95% CI. At least number and percentages of participants will be presented after vaccine injection reporting any:

- Immediate unsolicited systemic AEs
- Solicited injection site reactions and solicited systemic reactions occurring within 7 days after the day of injection (D1 to D8) according to presence, time of onset, intensity (Grade 1, Grade 2, or Grade 3), number of days of presence and action taken
- Unsolicited AEs occurring within 30 days after injection by system organ class (SOC) and preferred term (PT), relationship, intensity, time of onset, and duration
- All SAEs occurring throughout the study by SOC and PT, relationship and seriousness criteria
- All AESIs occurring throughout the study by SOC and PT and relationship

No replacement of missing data will be done. Nevertheless, missing relationship will be considered as related at the time of statistical analysis.

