4.3.1.1.2 Maximum Overall Intensity

Maximum overall intensity is derived from the daily intensities computed as described in [Section 4.3.1.1.1](#) and is calculated as the maximum of the daily intensities over the period considered.

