4.3.1.1.3 Presence

Presence is derived from the maximum overall intensity over the time period considered:

- None: No presence
- Grade 1, Grade 2, or Grade 3: Presence
- Missing or Unknown: Missing presence

Participants with at least one non-missing presence for a specific endpoint will be included in the analysis. Conversely, those without a non-missing presence will not be included in the analysis of the endpoint.

The time period is displayed as D01-D04, D05-D08, D09 and later.

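### The SAP drops a participant whose CRF reports a solicited reaction but who has no daily record; if such records occur, rates for the six reactions without a size cut-off are too low

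*SAP*

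**What the plan says.** SAP 4.3.1.1.1 derives daily intensities in two steps. Step 1 covers "Solicited reactions (except Fever/Pyrexia) with CRF presence recorded as" 'No': "with all daily records missing (Unknown) then all daily intensities will be derived as None". Step 2 covers everything else. For reactions that are not measured, "daily intensities will correspond to daily records reported in the clinical database"; for measured ones, the recorded sizes are converted to grades, and a size under 25 mm is graded None.

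SAP 4.3.1.1.2 defines the maximum intensity, "calculated as the maximum of the daily intensities over the period considered". SAP 4.3.1.1.3 derives presence from that maximum alone. Its last category reads "Missing or Unknown: Missing presence", and for participants in that category it adds: "Conversely, those without a non-missing presence will not be included in the analysis of the endpoint". SAP 5.5.1.3 on missing intensities refers solicited reactions back to these rules and adds nothing.

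Unsolicited AEs are handled differently. Under SAP 4.3.1.2.1 an observation is an event if it has a verbatim term and is not Grade 0. Under SAP 5.5.1.3 its missing intensity stays missing. In SAP 4.3.1.3.6, an unsolicited AE leading to discontinuation counts when its grade is missing, whereas a solicited one must be at least Grade 1.

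On data capture, Protocol 8.3.2 says: "Any information that was not documented in the diary card will first be captured in the source document and then reported electronically". On missing safety data, Protocol 9.4.2 says "No replacement of missing data will be done", with an exception for relationship, while SAP 5.5.1 allows imputation in a limited number of scenarios.

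**The concern.** The CRF presence answer is held separately from the daily records; otherwise step 1 would have nothing to act on. The SAP consults it in one direction only. A 'No' without daily records is used as an answer. A 'Yes' without daily records is ignored and the participant leaves the endpoint, so a reported reaction disappears from the table.

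Such a record is conceivable. The diary card is collected at Visit 2, D31 with a window of +14 days, which is 23 to 37 days after the solicited period ends on D08. At that interview a participant may remember having had a headache but not its grade on each day, and the site may enter information that the diary lacks.

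Presence of solicited injection-site reactions and presence of solicited systemic reactions are two of the five safety endpoints in SAP 4.1. They are reported as absolute percentages, so a selective loss of reactors goes straight into the estimate, and the exact confidence interval does not reflect it.

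**Working it through.** **Inputs.** The plan states no expected reaction rate, no rate of missing diaries, and not whether the CRF permits 'Yes' without daily entries. Its precision figures (SAP 5.2) concern log10 means in the PPAS and do not enter here. The group size of 150 is from SAP 5.2. The true rate p, and the share m of true reactors who have CRF 'Yes' and no daily record, are assumptions.

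**What the rules give when all daily records are missing (non-fever terms).**

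| CRF presence | Daily intensities | Presence | In numerator | In denominator |
|---|---|---|---|---|
| No | None (step 1) | No | no | yes |
| Yes | Missing (step 2) | Missing | no | no |

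**Formula for one reaction.** Of n participants, pn are reactors and pmn of these are dropped.

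- Reported rate = p(1−m)/(1−pm).
- Shift = p(1−m)/(1−pm) − p = −pm(1−p)/(1−pm). For p between 0 and 1 this is never positive, and it is zero when m = 0.
- Participants with 'No' and no daily records stay in as non-events, so their number does not affect the result.

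**Results at p = 50%.**

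- m = 2%: 0.49/0.99 = 49.5%, shift −0.5 points.
- m = 5%: 0.475/0.975 = 48.7%, shift −1.3 points.
- m = 10%: 0.45/0.95 = 47.4%, shift −2.6 points.

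At m = 10%, the shift is −0.9 points for p = 10%, −2.2 for p = 30% and −2.3 for p = 70%.

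**Example in whole participants.** With 150 participants, 75 reactors and 4 of them 'Yes' without daily records, the SAP rule gives 71/146 = 48.6%. Counting the four as present gives 75/150 = 50.0%. Dropping 'No' without daily records as well would not be neutral: with 10 such participants it gives 71/136 = 52.2%.

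**Composite endpoints.** Suppose 'any injection-site reaction' keeps a participant because another component is None. Let m now be the share of composite reactors whose only positive component is a 'Yes' without daily records. The rate is then p(1−m): at p = 50%, 47.5% (−2.5 points) for m = 5% and 45.0% (−5.0) for m = 10%. The SAP does not spell out this case.

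**Erythema and swelling.** Take 15/150 = 10.0% truly at 25 mm or more, and 4 participants with 'Yes' and no sizes.

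- Half of the four at or above 25 mm: 13/146 = 8.9%.
- A quarter: 14/146 = 9.6%.
- None: 15/146 = 10.3%, an upward shift.

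**Differences between arms.** For true rates of 60% and 40% with equal m, the difference is 58.76 − 38.78 = 19.99 points at m = 5% (from unrounded rates) and 57.45 − 37.50 = 19.95 points at m = 10%.

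**Scale.** The exact 95% interval for 75/150 is 41.7% to 58.3%.

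**The case against.** The strongest reply is that the problem may never arise. Neither document says the CRF accepts 'Yes' without daily entries. At Visit 2 the site interviews the participant and tries to clarify incomplete entries, and Protocol 8.3.2 lets the site supply the missing grade just as it lets it supply the 'Yes'. This stands as a limit on size: the bias is conditional. It does not supply the missing rule.

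A second reply is that the SAP lets daily records govern; SAP 4.3.1.1.7, for instance, sets aside the investigator's ongoing flag in favour of the measurement. That stands where daily records exist, and a participant with eight recorded None days should not be overridden. It does not help where there is no record to govern.

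A third is that the analyses are descriptive and the shift is small against the interval. That is correct for any single rate.

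Three stronger readings are tempting, and the documents do not support them.

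- A reader might infer that treating 'No' as None is itself a favourable imputation that breaches Protocol 9.4.2. A recorded 'No' is data, its frequency cancels out of the rate, and Protocol 9.4 leaves technical detail to the SAP. The fault is the absent counterpart for 'Yes'.
- A reader might infer that a 'Yes' with the reaction day blank and the other days None is counted as no reaction. The SAP does not say how None and Missing rank when the maximum is taken, so this is a gap and not a stated rule.
- A reader might add the reactions that participants forget by Visit 2. That is recall error, which no classification rule removes.

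**Conclusion.** The point holds in a conditional form. The SAP has a stated rule that removes a participant with CRF 'Yes' and no daily record from a solicited-reaction endpoint, nothing elsewhere in the SAP restores that participant, and an unsolicited AE with the same gap is kept.

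For the six terms without a size cut-off, the error can only be downward. With p = 50% and m up to 10%, it reaches 2.6 points for a single reaction. Both p and m are assumed, and the calculation takes a CRF 'Yes' to be a true reaction.

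The documents do not show that every non-fever rate is biased by construction. With no such records the bias is zero; for erythema and swelling it could go either way; and comparisons between formulations barely move if m is the same in each arm. This is a modest but real defect in how absolute reactogenicity is reported, and it is cheap to remove.

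**What to change.** Amend SAP 4.3.1.1.1 to 4.3.1.1.3 as follows.

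- **Pain, headache, malaise, myalgia, arthralgia, shivering:** where CRF presence is 'Yes', no daily record is Grade 1 or more and at least one daily record is missing, set presence to Yes and maximum intensity to Missing. Leave eight recorded None days as they are.
- **Erythema and swelling:** where all sizes are unknown, keep presence Missing, and add one sensitivity row that counts 'Yes' as present.
- **Ranking:** state how a mix of None and Missing days is resolved when the maximum is taken.
- **'No' rule:** keep it, and note in the SAP that it is a deliberate use of the CRF answer, so that it reads consistently with Protocol 9.4.2.
- **Reporting:** give the number of participants per arm classified by each rule.

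The cost is a few sentences and a small programming change, with no new data. Reported rates may rise slightly, and the intensity tables gain a Missing row. If the counts are zero, no rate changes, and the report can say so.
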